6 STUDY DESIGN

6.1 Overall Study Design and Plan

This is a phase 1, single-centre, single-group, nonrandomised, noncomparative, open-label, single-dose study to evaluate the safety, biodistribution, internal radiation dosimetry, and ED of DaTSCAN™ ioflupane (^{123}I) injection in Chinese HVs. Eight evaluable subjects (4 males and 4 females) will be included in the study. The study will be conducted at a single centre in the People's Republic of China.

The study will consist of a minimum of 3 visits for each subject. Each subject will attend a screening visit within 20 days before injection, an imaging visit, and a follow-up visit approximately 2 weeks after injection. During the screening visit, the subjects must satisfy all entry criteria and undergo safety assessments.

During the imaging visit, each subject will receive, by bolus IV administration, a single dose of ioflupane (^{123}I) injection with a nominal iodine (^{123}I) activity of $111\text{ MBq} \pm 10\%$ and will undergo simultaneous whole-body (head to mid-thigh) anterior and posterior planar scintigraphy scans at 10 minutes, 1 hour, 2 hours, 4 hours, 5 hours, 24 hours, and 48 hours after administration. Brain SPECT imaging will be performed at 3 and 6 hours after administration. A reference source will be imaged alongside the subject. Time-activity curves will then be generated from ^{123}I activity data from all 8 subjects and integrated to obtain the normalised-cumulated activity in each source region, which will then be used along with the Medical Internal Radiation Dosimetry (MIRD) schema to determine the internal radiation dosimetry. The dosimetry will be evaluated for the Cristy-Eckerman female and hermaphrodite male phantoms.

For evaluation of the biodistribution and radiation dosimetry, blood (up to 5 mL) samples will be collected at 1 hour before administration of ioflupane (^{123}I) injection and at the following times after administration of IMP: 5, 15, 30 minutes and 1, 2, 3, 4, 5, 24, and 48 hours. Urine excreted from 1 hour before administration of ioflupane (^{123}I) injection to 48 hours after administration will be collected as voided.

At the follow-up visit, all subjects will undergo specified safety assessments, and all female subjects of childbearing potential will also have a urine pregnancy test.

[figure not shown]
All subjects' safety will be monitored during the course of the study. The safety analysis will include the following:

- AEs up to study exit.
- A tolerability questionnaire to be completed at approximately 1 hour before injection and at approximately 15 minutes, 1, 4, 24, 48 hours after injection.
- Physical examination at prespecified time points.

- Clinical laboratory tests (serum biochemistry, haematology, and urinalysis) at screening visit (which will be considered baseline), and at approximately 3 hours, 48 hours, and 2 weeks after injection.
- Injection site monitoring (at baseline, at approximately 1 hour before injection, and at approximately 4 hours after injection).
- Vital signs and oxygen saturation (at screening visit; at baseline; at approximately 1 hour before injection; and at approximately 10, 20, and 30 minutes; approximately 1, 2, 4, 24, and 48 hours; and approximately 2 weeks after injection).
- 12-lead electrocardiogram (ECG) (at screening visit, at approximately 1 hour before injection, and at approximately 2 and 5 hours after injection).
- Concomitant medications.

An overview of study procedures is presented in [Figure 1](#).

Figure 1 Study Diagram

6.2 Study Rationale

The quantity of ioflupane in the 5 mL formulation of DaTSCAN™ ioflupane (^{123}I) injection is 0.625 μg . The pharmacokinetics of DaTSCAN™ ioflupane (^{123}I) injection has been studied in healthy adults. Because administration is IV, absorption is complete and ioflupane (^{123}I) is completely bioavailable.

The pharmacokinetics of DaTSCAN™ ioflupane (^{123}I) injection were studied by monitoring radioactivity after IV injection. Similar studies have already been done to evaluate the pharmacokinetics of DaTSCAN™ ioflupane (^{123}I) injection in European subjects [Study CY 95.FP.1], [Frear 1998] and Japanese subjects (Study NMA98P1 [Takano et al 1999]). The current study will involve Chinese subjects.

In this study, anterior and posterior whole-body images will be obtained by using a 2-headed gamma camera at 10 minutes, 1 hour, 2 hours, 4 hours, 5 hours, 24 hours, and 48 hours after injection of DaTSCAN™. A dual-head scintillation camera, medium-energy collimator, and standard imaging techniques will be used. An external ^{123}I calibration source will be imaged alongside the subject.

Biodistribution of ^{123}I after administration of DaTSCAN™ will be measured by whole-body imaging in conjunction with serial blood and urine sampling. From regions of interest (ROIs) placed upon conjugate anterior and posterior whole-body images, the activities in the brain, striatum, thyroid, lungs, liver, spleen, stomach, heart, and intestines will be determined. The data will be used to calculate initial organ uptake, normalised cumulative activity, absorbed organ dose and the ED, according to the methodology of MIRD [Siegal et al 1999] and the International Commission on Radiological Protection (ICRP) [ICRP 1991].

6.2.1 Rationale for Administered Radioactivity

It is planned that the administered radioactivity will be $111 \text{ MBq} \pm 10\%$. This is less than the 111 to 185 MBq recommended for clinical DaTSCAN™ SPECT but is sufficient, according to previous experience, for planar imaging to determine biodistribution and dosimetry while minimising radiation exposure to HVs.

6.2.2 Rationale for Safety Monitoring Plan

Safety assessments will be performed at screening, before and after administration of IMP, and approximately 2 weeks after administration of IMP. The planned safety assessments are designed to ensure subject safety and to identify and minimise unnecessary risks.

This study's safety monitoring plan is justifiable and adequate from a safety standpoint in view of the following:

- The design of the safety plan permits a comparison of the safety variables at baseline (in this study baseline period is defined as “after the screening visit up to 1 hour prior to administration” except clinical laboratory tests, of which baseline value is that taken during

screening visit) and after IV injection of DaTSCAN™ ioflupane (¹²³I) injection in the same subject.

- Safety variables collected in the present study can be compared with safety variables from other related studies.
- The 2-week safety monitoring permits the evaluation of late-appearing adverse events (AEs) that may emerge or progress after the administration of DaTSCAN™ ioflupane (¹²³I) injection.
- Evaluation of the safety database held by the sponsor (which includes clinical study data as well as post marketing data in the United States and Europe) does not show any new safety signals that would require a modification of the safety assessments as planned.
- The measures used to assess safety are well defined and reliable, and the proposed safety analyses are adequate to assess the effects of the administration of ioflupane (¹²³I) injection in HVs.

6.3 Study Timeframe

The study is expected to begin enrolment in 2020. The start of the study is defined as the point at which all necessary regulatory and local approvals are in place, the study centre staff have been adequately trained, and the study centre has sufficient resources available to start enrolling subjects. The end of the study is defined as the date of last subject last visit.

Each subject's participation will consist of 3 study visits. The screening visit may take place up to 20 days before IMP injection. The imaging visit will last approximately 48 hours, followed by a follow-up visit approximately 2 weeks after IMP injection.

6.4 Risks and Benefits to Subjects

As is true for many phase 1 studies, there are no expected direct benefits to HVs who will be subjects in this trial. However, data collected from study participants may help others (especially patients) prospectively by contributing to a knowledge base for further evaluation of the use of DaTSCAN™ ioflupane (¹²³I) injection.

The risks to subjects mainly relate to the IV injection and the radiation emitted by the drug. From previous experience, IV injection is known to carry a small risk of infection and haematoma. This risk is not related to the IMP but to the procedure itself. IV lines will be placed and monitored by qualified personnel in order to minimise risk to the subjects.

DaTSCAN™ is a radiopharmaceutical. As such, it exposes the recipient to ionising radiation. However, previous studies have shown that the effective radiation dose is 21 to 24 μ Sv/MBq, so the dose for this procedure is approximately 2.7 mSv, which is slightly over the published annual ED equivalent from natural radiation in China [Ziquiang et al 1994]. As the product is a radiopharmaceutical intended for diagnostic use, evaluation of dosimetry estimates is

mandatory for a marketing authorisation. Therefore, administration of a radioactive dose is unavoidable. However, the dose chosen for this study is based on previous experience to ensure that useful images can be obtained while minimising the radiation exposure to the HV. Administration of a radioactive dose that would not yield useful evaluable images would be unethical.

7 SELECTION AND WITHDRAWAL OF SUBJECTS

7.1 Procedures for Enrolment

The subjects will be recruited by means accepted by the respective regulatory bodies/local health authority (in accordance with local regulations) and the local Independent Ethics Committee (IEC).

A maximum of 8 evaluable subjects (HVs) will be enrolled. A written and dated informed consent form will be obtained from all subjects prior to any protocol specific procedures being performed.

Each potential subject will attend the clinical site for a screening visit within 20 days before IMP administration to ensure that they fulfil the study entry criteria. Each subject will be given a unique identification number. The identification number will be assigned to the subject during the screening visit, after the informed consent document has been signed and dated. Once an identification number has been assigned, it cannot be reassigned, even if the subject is deemed ineligible or withdraws consent. No subject may enter the study more than once.

Subjects withdrawing before IMP administration (i.e., a non-evaluable subject) will be replaced. Additional subjects may be enrolled to reach the required number of evaluable subjects within each step (see Section 6.1). Replacement subjects will be assigned unique subject numbers.

7.2 Inclusion Criteria

To be included in this study, a subject will have to meet all of the following criteria:

- (1) Chinese male or female who has agreed to sign and date the written informed consent form
- (2) Age 18-70 years
- (3) Body mass index (BMI) of 18-30 kg/m²
- (4) General good state of health as judged by a qualified physician after completing physical examination
- (5) Fit, co-operative, and able to provide consent

7.3 Exclusion Criteria

Subjects are to be excluded from this study if they meet any of the following criteria:

- (1) Sensitivity to DaTSCAN™ ioflupane (¹²³I) injection or any of its ingredients

- (2) A history of motor disturbances
- (3) A history of pulmonary, cardiovascular, neurological, renal or hepatic, hormonal or coagulation disorders or hyperthyroidism
- (4) A history of drug, alcohol, or solvent abuse
- (5) The subject has been previously enrolled in this study or participated in a clinical study involving an investigational pharmaceutical product within 30 days prior to screening
- (6) Radionuclide injection within a minimum of 5 radioactive half-lives prior to screening
- (7) Use of any medication (except paracetamol [acetaminophen] or oral contraceptive), including traditional Chinese medicine, within 2 weeks prior to the imaging visit
- (8) Classification as a radiation worker
- (9) Women of child-bearing potential not accepting a highly effective method of birth control (A woman is considered of child-bearing potential, i.e., fertile, following menarche and until becoming post-menopausal unless permanently sterile. Permanent sterilisation methods include hysterectomy, bilateral salpingectomy and bilateral oophorectomy. Postmenopausal is defined as 12 months with no menses without an alternative medical cause, in International Council on Harmonisation (ICH) M3 (R2); A highly effective method of birth control is defined as one which results in a low failure rate (i.e., less than 1 % per year) when used consistently and correctly, such as implants, injectables, combined oral contraceptives, some intrauterine devices, sexual abstinence or vasectomised partner, in ICH M3 (R2).)
- (10) Pregnant or lactating women

7.4 Withdrawal and Termination Criteria

7.4.1 Subject Withdrawal

There are no formal withdrawal criteria for this study. During the conduct of the study, the sponsor or its designee will review the safety data for trends and signals that would indicate the need for withdrawal of a subject.

In accordance with the Declaration of Helsinki, each subject is free to withdraw from the study at any time. Investigator(s) also have the right to withdraw subjects from the study in the event of illness, AEs, or other reasons concerning the health or well-being of the subject, or in the case of lack of co-operation.

Should a subject decide to withdraw after administration of the IMP, or should the investigator(s) decide to withdraw the subject, all efforts will be made to complete and report the observations up to the time of withdrawal as thoroughly as possible. A complete final

evaluation at the time of the subject's withdrawal should be made and an explanation given of why the subject is withdrawing or being withdrawn from the study.

The reason for withdrawal must be noted in the Case Report Form (CRF). If the reason for withdrawal is an AE, the specific event or test result(s) must be recorded in the CRF. If the subject discontinues for a serious AE (SAE), such as hospitalization, the subject data will be collected and monitored until the outcome is evident. If the event has ended, the stop date of the event will be recorded in the CRF. If the event is still ongoing, the outcome of the event must be Ongoing or Not Yet Resolved. An outcome of Unknown is not acceptable, even if the event is ongoing on the date of study discontinuation.

Subjects who withdraw from the study before the study procedures are complete will be replaced.

7.4.2 Study or Site Termination

The sponsor reserves the right to terminate the study at any time.

8 TREATMENT OF SUBJECTS

8.1 Investigational Medicinal Product

8.1.1 DaTSCAN™ Ioflupane (¹²³I) Injection

DaTSCAN™ ioflupane (¹²³I) injection is a clear, colourless ethanolic solution for IV injection. It is provided in a 5-mL vial for our study.

The active ingredient in DaTSCAN™ ioflupane (¹²³I) injection is ioflupane (¹²³I). The 5.0 mL vial contains 370 MBq at reference time in 5.0 mL of solution. The radionuclidic purity is >99%. The radiochemical purity is $\geq 96\% [{}^{123}\text{I}]$ ioflupane at release, $\geq 94\% [{}^{123}\text{I}]$ ioflupane at expiry; $\leq 4\% [{}^{123}\text{I}]$ iodide at release, $\leq 6\% [{}^{123}\text{I}]$ iodide at expiry. The expiry time is 20 hours after the activity reference time stated on the label for the 5.0-mL presentation. Inactive ingredients include nonradioactive ioflupane (0.1 $\mu\text{g}/\text{mL}$), acetic acid (5.5 mg/mL), sodium acetate (7.8 mg/mL), ethanol (5% v/v), water for injection, to 5 mL.

Like other radiopharmaceuticals, DaTSCAN™ ioflupane (¹²³I) injection should be used only by qualified personnel with the appropriate government authorisation for the use and manipulation of radionuclides within a designated clinical setting. Appropriate radiation precautions should be observed during the preparation and storage of the agent. The product should be stored at room temperature and should never be frozen.

Handling of the material and spill clean-up and disposal will be performed in accordance with local regulations and local practice in the nuclear medicine department.

In this study, each subject will receive 1 dose of DaTSCAN™ ioflupane (¹²³I) injection. Each subject will receive a dose of 111 MBq $\pm 10\%$, in a maximum volume of 5 mL. To minimise pain upon injection, the dose will be delivered by a slow IV injection (not less than 15 to 20 seconds) into an arm vein.

8.1.2 Supply and Packaging

DaTSCAN™ ioflupane (¹²³I) injection is provided in a properly labelled, single-use 5-mL vial.

8.1.3 Stability and Storage

The IMP should be stored at room temperature (<25°C, no freezing). During both storage and dose preparation, appropriate radiation precautions should be observed.

8.1.4 Comparator

No comparator is to be used in this study.

8.1.5 Thyroid Blocking

To minimise thyroid uptake of radioactive iodine, subjects must undergo appropriate thyroid blocking, according to local practice, prior to and after administration of the IMP. For example, potassium iodide tablet (approximately 120 mg) or potassium iodide oral solution/Lugol's solution (equivalent to 100 mg iodide) or potassium perchlorate (400 mg) may be used for blockade of the thyroid gland, to be administered within 1 to 4 hours prior to and 12 to 24 hours after injection of DaTSCAN™.

The thyroid blocking agent will be preferably sourced locally by the hospital. If it is not available in the hospital, then sponsor/contract research organisation (CRO) should provide it. The administered time, date and dose will be captured on the concomitant medication page of CRF.

8.1.6 IMP Accountability

Each investigator is responsible for ensuring that deliveries of IMP(s) and other study materials from the sponsor are correctly received, recorded, handled, and stored safely and properly in accordance with all applicable regulatory guidelines, and used in accordance with this protocol.

All IMP containers (opened, unopened, or empty) must be destroyed on site after IMP administration for each subject; the site has the option to use external destruction services if preferred. The overall drug accountability must be completed by the sponsor or representative. A list of IMP(s) and other materials that were destroyed, must be prepared and signed by the principal investigator or designee. If there are any discrepancies, an explanation for these should also be provided.

The current Investigator's Brochure for the IMP will be supplied to the site.

8.1.7 Registration of Investigational Medicinal Product Complaints

In the event of an IMP complaint (e.g., breakage, leakage, particulate matter, discolouration), the investigator or recipient of the IMP is requested to report the problem on the IMP shipping documentation (e.g., 'Delivery Note for Product', Drug Shipping and Receiving Form, or equivalent form). This report should be promptly forwarded to the person indicated on the shipping documentation. Once the report is received, the Clinical Supplies Manager will register the complaint and determine if the complaint is minor or significant, according to sponsor procedures. All complaints will be followed up, and the appropriate action will be implemented according to sponsor procedures.

8.2 Method of Numbering Subjects and Assigning Subjects to Treatment Groups

This is an open-label noncomparative study. Thus, there will be no randomisation or assignment to treatment groups. However, all subjects will be assigned a unique study number to protect their privacy.

8.3 Selection of Doses and Timing

In this study, each of the subjects will receive 1 dose of DaTSCAN™ ioflupane (^{123}I) injection. The subjects will receive a dose at the lower end of the approved dose range in Europe and the United States. The dose in this study will be $111 \text{ MBq} \pm 10\%$, in a maximum volume of 5 mL. This dose was used in the phase 1 study (CY95.FP.I) conducted in Europe.

The dose is to be delivered by slow bolus (15 to 20 seconds) IV injection; aseptic technique will be used during the administration.

8.4 Blinding

This is an open-label study. Therefore, there will be no blinding.

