10.2.2 Assessment of Striatal Binding Ratio

Left and right striatal binding ratios (SBR) will be determined from brain SPECT images acquired at 3 and 6 hours after administration.

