10.2.4 Image Interpretation and Correlation with Standard of Truth

Images obtained will be analysed by using ROIs in order to quantify counts in the organs of interest at prespecified time points. There will be no standard of truth in this trial as it is not a trial to assess diagnostic efficacy.

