12.6 Secondary Analysis

12.6.1 Biodistribution

By using activity data from ROIs, data from the whole-body images, as well as activity data from serial blood and urine samples, descriptive statistics will be generated for biodistribution data (decay-corrected percentage administered activity per organ) at each time point for each organ and tissue of interest in HVs. Time-activity curves will then be generated from ^{123}I activity data from all 8 subjects and integrated to obtain the normalised-cumulated activity in each source region, which will be summarised with descriptive statistics. The amount of ^{123}I activity in plasma and excreted in urine will be calculated from the product of concentration of ^{123}I activity measured in each sample and the volume of each sample.

The cumulative amount of ^{123}I activity excreted in urine will be tabulated for each subject and summarised. In addition, the normalised cumulative activity in each source region will be compared between the Chinese subjects from this study and European subjects by using the 2-sample t-test.

SBR will be analysed to determine the stability of striatal uptake relative to a reference region over the proposed imaging window of 3 to 6 hours after administration. The difference

between the SBR at 3 and 6 hours calculated for each subject will be tested by Wilcoxon signed-rank test.

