12.8 Sample Size Calculation

No sample size calculations were performed. The number of subjects in this study was determined to fulfil local regulatory requirements.

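### Nothing in the supplied text masks scan time when SBR is quantified, although the 3 h versus 6 h comparison is meant to show stability

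*Combined protocol and SAP*

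**What the plan says.** All references are to the combined protocol and SAP.

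- **Blinding.** Section 8.4, within Section 8 on treatment of subjects, reads "This is an open-label study. Therefore, there will be no blinding".
- **What is measured.** Section 10.2.2: "Left and right striatal binding ratios (SBR) will be determined from brain SPECT images acquired at 3 and 6 hours after administration".
- **How images are quantified.** Section 10.2.4: "Images obtained will be analysed by using ROIs in order to quantify counts in the organs of interest at prespecified time points".
- **Purpose.** Section 12.6.1: "SBR will be analysed to determine the stability of striatal uptake relative to a reference region over the proposed imaging window of 3 to 6" (in hours from dosing). The summary of Amendment A01 (Section 16.1.2) gives the reason for adding the two scans: to support the label's imaging window.
- **Test.** Section 12.6.1: the difference "between the SBR at 3 and 6 hours calculated for each subject will be tested by Wilcoxon signed-rank test".
- **Sample size.** Section 6.1: "Eight evaluable subjects (4 males and 4 females) will be included in the study". Section 12.8: "No sample size calculations were performed. The number of subjects in this study was determined to fulfil local regulatory requirements".
- **Imaging Manual.** Sections 9.2.3, 10.2.1.1 and 15.2 refer to a separate Imaging Manual for imaging details. It is not among the documents supplied.

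**The concern.** Section 8.4 argues from open-label dosing to no blinding, without qualification. For the SBR question that step does not follow. The comparison is between two scans of the same person after the same dose. Knowing that the product was given does not require whoever quantifies the images to know which scan came first, so scan time can be masked in an open-label study.

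It matters because the favourable answer here is no difference. SBR is a ratio of striatal to reference-region uptake, so where the regions are placed affects the value. If placement leaves room for judgement, a person who knows the time points and expects stability may, without intending to, bring the two values closer together. In a conventional superiority comparison, that kind of error works against the hoped-for result. Here it works towards it, with only 8 pairs.

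**Working it through.** **Step 1. What the text provides on masked reading.**

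| Question | Supplied text |
|---|---|
| Is scan time masked when SBR is quantified? | Not stated. 8.4 rules out blinding in general terms |
| Is the order of quantification randomised? | Not stated |
| Are regions manual, templated or automated? | Not stated. 10.2.4 says only that regions of interest are used |
| Who places them, and how many times? | Not stated |
| Is any step blinded? | Yes: decisions on excluding subjects or values (12.11), not image quantification |
| Is any sensitivity analysis planned? | None (12.6.6) |

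Section 12.11 shows that the plan sees a use for masking in a single-group, open-label study. It does not extend it to this measurement.

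**Step 2. Number of data sets.** 8 subjects (6.1) × 2 SPECT scans (10.2.2) = 16.

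**Step 3. The test at n = 8.** The plan gives no power, effect size, SD or significance level for this comparison, so there is no figure of its own to reproduce. I assume a two-sided 5% level. Under the null there are 2^8 = 256 equally likely sign patterns. The patterns with a rank sum of 0, 1, 2 or 3 number 1 + 1 + 1 + 2 = 5, so rejecting when the smaller rank sum is at most 3 gives an exact level of 2 × 5/256 = 0.0391. Two further patterns sum to 4, and including them would give 2 × 7/256 = 0.0547, above 5%.

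**Step 4. Illustration of a reading bias.** Assumptions, none from the documents: normal paired changes, a true mean drift of δ = 1 SD of the paired change, and a reading bias that takes a fraction f of that drift off every subject's change and leaves the spread as it was. The remaining drift is (1 − f)δ. Rejection rates from 200,000 simulated trials per value:

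| f | Remaining drift (SD) | Rejection rate |
|---|---|---|
| 0 | 1.00 | 0.61 |
| 0.25 | 0.75 | 0.385 |
| 0.50 | 0.50 | 0.19 |
| 0.75 | 0.25 | 0.075 |
| 1 | 0 | 0.039 |

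If reading halves the drift, power falls from 61% to 19%.

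**Step 5. Limit of the illustration.** It depends on the form of the bias. Had reading instead multiplied each subject's change by one half, the SD would halve too. The signed-rank result would then be unchanged, because ranks do not depend on scale, but the estimated drift would still be half the true one. The documents give no information on reading error with which to choose between these forms.

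**Step 6. Left and right.** Section 10.2.2 yields two values per subject per time point, and 12.6.1 tests a difference for each subject. The rule that turns two sides into one value is not written down. If it is the left-right mean, there is one difference per subject and the exact level in Step 3 applies.

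**The case against.** There is a fair case on the other side.

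- **Section 8.4 concerns treatment.** It sits beside dose selection and subject numbering and does not mention image reading. A reader might infer that the sponsor decided to quantify the scans unmasked. The documents do not support that: they are silent on the point. This objection stands, and it is a reason to say in 8.4 that it covers treatment only.
- **The Imaging Manual may already cover it.** It may fix a template, a reading order or masking. That also stands as a possibility. However, the protocol introduces the manual under image acquisition and never says that it governs masked quantification. If it does, a cross-reference settles the matter.
- **Operator discretion is assumed.** If the regions are placed automatically, expectation has little room to act. The documents do not say how they are placed, so the concern is conditional.
- **The test is not confirmatory** (12.5, 12.6.4). True, but a biased measurement distorts a descriptive estimate as much as a p-value, and Section 16.1.2 ties these scans to label wording.
- **The larger weakness is the test itself.** Even with unbiased reading, a 1 SD drift would be missed 1 − 0.61 = 39% of the time, so non-significance does not show stability. That is right, but it is a separate issue that masking neither causes nor cures.

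**Conclusion.** The point holds as a gap in measurement safeguards. The supplied text does not mask scan time for a comparison whose purpose is to show agreement between two time points, and open-label dosing does not justify leaving it unmasked. Whether bias would occur depends on operator discretion, which is undocumented. Its size and direction cannot be derived from the documents. The fall in power from 61% to 19% rests on the assumed 1 SD drift, a reading bias that removes half of it with spread unchanged, normal changes, n = 8 and a two-sided 5% level. It shows how sensitive the comparison could be and is not an estimate of what will happen.

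Two stronger readings are tempting, and neither is supported. From 10.2.2 a reader might infer that left and right enter the test as 16 separate pairs, which would overstate the information. Section 12.6.1 refers to a difference for each subject, most naturally one value each, and nothing proposes 16. A reader might also infer that one striatum is discarded and avoidable noise is left in, but nothing says that a single side is used. What remains is a missing sentence on how the two sides are combined, which is a minor clarification.

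**What to change.** 1. **Section 8.4:** limit the statement to treatment.
2. **Section 10.2.2:** state that the 16 SPECT data sets are quantified in random order with subject and time labels removed, using one volume-of-interest template fixed before any data set is quantified. If the Imaging Manual already requires this, cite the section instead.
3. **Section 12.6.1 (minor):** define each subject's SBR at each time point as the mean of left and right, and show each side descriptively.

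The cost is relabelling 16 files and a few sentences of text. No extra reader, scan or subject is needed.
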